### **12.3. Contact lens Corrected Visual Acuity**

Contact lens visual acuity will be assessed using Snellen visual acuity Charts at both 4m (Distance) and 40cm (Near) at the fitting evaluation, lens dispensing, 3-day follow-up and the 2-week Follow-up evaluations. CLVA will be assessed both monocularly and binocularly. Summaries for Monocular CLVA and binocular CLVA will be presented using counts and percentages of eyes and subjects, for monocular CLVA and binocular CLVA, respectively.

### **12.4. Reasons for Discontinuation**

The number of discontinued subjects by the analysis time point will be displayed by visit.

Reasons for discontinuation include the following:

1. Adverse Event
2. Unsatisfactory lens fitting due to test article
3. Unsatisfactory visual response due to test articles

4. Lens discomfort
5. Withdrew consent during study
6. Lost to follow-up
7. Subject no longer meet eligibility criteria
8. Subject withdrawn by PI due to non-compliance to protocol
9. Test article no longer available
10. Other

## **12.5. Unscheduled Lens Replacement**

The number of unscheduled lens replacements and corresponding reasons will be tabulated by visit and overall, across eyes for both completed and discontinued eyes.

## **12.6. Physical Examination Findings**

Slit lamp findings will be assessed for each subject eye at baseline, 3-day Follow-up, the 2-week follow-up and at any unscheduled visit using the FDA Grading scale (Grade 0=None, Grade 1=Trace, Grade 2=Mild, Grade 3=Moderate, Grade 4=Severe). Slit lamp finding assessments include the following metrics:

- Corneal Infiltrates (Yes/No)
- Corneal Edema
- Corneal Neovascularization
- Corneal Neovascularization Location
- Corneal Staining
- Corneal Staining Location
- Conjunctival Injection
- Tarsal Abnormalities
- Other

## **12.7. Clinical Laboratory Tests**

Not applicable.

## **12.8. Other Safety Parameters**

### Subject's Reported Ocular Symptoms

Frequency and severity by eye of subject's reported ocular symptoms and problems with the study lens at fitting and post-fitting evaluation visits including the 2-Week Follow-up and unscheduled visits. Severity of the symptoms can be:

- 0 = Not Applicable or Not Recorded;
- 1 = Mild and results in little or no interference with lens wear;
- 2 = Moderate AND/OR occasionally interferes with lens wear;
- 3 = Severe AND/OR frequently interferes with lens wear.

### Lens fitting characteristics

Frequency by eye of mechanical lens fitting characteristics at fitting and 2-Week Follow-up evaluations. Lens fitting characteristics to be reported are:

- Lens Centration Grade
- Decentered Direction
- Limbal Exposure Grade
- Edge Lift (Present or Absent)
- Primary Gaze Movement Grade
- Upgaze Movement Grade
- Lens Tightness Grade (Push-up Test)
- Acceptable Fitting (yes/no)

### Contact Lens Deposits

Contact lens deposits will be assessed for each eye at the 2-week Follow-up on the front and back surface of the study lens; the amount of deposits will be Graded using the scale:

- None = Grade 0 (No deposition).
- Slight = Grade 1 (Deposition which occupies 1-5% of the lens surface area.)
- Mild = Grade 2 (Deposition which occupies 6-15% of the lens surface area.)
- Moderate = Grade 3 (Deposition which occupies 16-25% of the lens surface area.)
- Severe = Grade 4 (Deposition which occupies =26% of the lens surface area.)

### Contact Lens Wettability

Contact lens Wettability will be assessed for each eye at the 2-week Follow-up. Wettability will be Graded using the scale:

- Grade 0 = All regions of lens surface are wettable between blinks (a minimum of 6 seconds between blinks).
- Grade 1 = Discrete non-wetting area(s) after a minimum of 3 seconds post blink.
- Grade 2 = Single non-wetting area within 2-3 seconds of blink.
- Grade 3 = Several non-wetting areas within 2-3 seconds of blink.
- Grade 4 = Immediate area(s) of non-wetting after blink.

## 14. APPENDICES

### 14.1. Time and Event Schedule

Visit Information	Visit 1 Screening, Baseline, Treatment 1 Fitting	Visit 2 Treatment 1 Follow-up 1 Optimization	Visit 3 Treatment 1 Follow-up 2
Time Point	Day 0	Day 3±1 from V1	Day 12±2 from V2
Estimated Visit Duration	2.5 hours	1.0 hours	1.5 hours
Statement of Informed Consent	x		
Demographics	x		
Medical History/Concomitant Medications	x		
Adverse Events and Concomitant Medications Review		x	x
Compliance		x	x
Habitual Contact Lens Information	x		
Contact Lens History	x		
Wear Time and Comfortable Wear Time with Habitual Lenses	x		
Wear Time and Comfortable Wear Time with Study Lenses		x	x
Screening Inclusion/Exclusion Criteria	x		
Subject Reported Ocular Symptoms	x	x	x
Baseline Questionnaire	x		
CLDEQ-8 Questionnaire	x	x	x

Visit Information	Visit 1 Screening, Baseline, Treatment 1 Fitting	Visit 2 Treatment 1 Follow-up 1 Optimization	Visit 3 Treatment 1 Follow-up 2
Time Point	Day 0	Day 3±1 from V1	Day 12±2 from V2
Estimated Visit Duration	2.5 hours	1.0 hours	1.5 hours
Distance and Near Entrance Visual Acuity	x	x	x
Lens Removal	x	x	x
Keratometry	x		
Subjective Refraction and Distance Visual Acuity	x		
Near ADD Determination	x		
Ocular Dominance	x		
ADD Refinement	x		
Near Visual Acuity	x		
Biomicroscopy	x	x	x
Baseline Inclusion/Exclusion Criteria	x		
Eligibility	x		
Lens Selection	x	x (if modified)	
Lens Insertion	x	x	x
10 Minute Settling	x	x (if modified)	
Visual Satisfaction / Subjective Acceptance	x	x	x
Study Lens Distance and Near Visual Acuity	x	x	x
Distance Over Refraction and Visual Acuity	x	x	
Lens Fit Assessment	x	x	x
Binocular Over Refraction		x	x
Lens Deposits			x
Lens Wettability			x

Visit Information	Visit 1 Screening, Baseline, Treatment 1 Fitting	Visit 2 Treatment 1 Follow-up 1 Optimization	Visit 3 Treatment 1 Follow-up 2
Time Point	Day 0	Day 3±1 from V1	Day 12±2 from V2
Estimated Visit Duration	2.5 hours	1.0 hours	1.5 hours
Visual Performance			X
Modifications	X	X	
Post-Fit GSI Questionnaire	X	X	
Worn Lens Collection		X	X
Study Lens Questionnaire		X	X
Distance and Near Exit Visual Acuity	X	X	
Dispensing Criteria	X	X	
Instructions	X	X	
Schedule Follow-up	X	X	
Final Evaluation			X (or when subject discontinued)

## 14.2. Statistical Analysis Code

### 14.2.1. Primary Analysis

#### CLUE Vision

```
PROC MCMC DATA =ads NTHREADS =12 SEED =18965237 NBI =15000 NMC
=100000 THIN=20 DIAG = ALL OUTPOST = simout DIC PLOTS(SMOOTH FRINGE) =
ALL MCHISTORY = BRIEF PROPCOV = QUANEW STATS = ALL STATS(ALPHA =
(0.05) PERCENTAGE = (2.5 50 97.5)) plots(smooth)=ALL MONITOR=(_parms_
Hyperopes_3day Myopes_3day Hyperopes_2wk Myopes_2wk);
```

```
ARRAY aval[2] FU1 FU2;
ARRAY mu[2] mu1 mu2;
ARRAY sigma[2,2];
ARRAY S[2,2] ( 1 0
0 1 );
```

```
PARMS p1 0.5 p2 0.1 beta0-beta5 ;
```

```
PARMS sigma { 1 0
0 1 };
PARMS sigma_site;
```

```
PRIOR beta: ~ NORMAL(0, var = 1000);
```

```
prior p: ~ NORMAL(0, var=1000);
```

```
PRIOR sigma ~ IWISH(2, S);
```

```
PRIOR sigma_site ~ IGAMMA(shape = 0.01, scale = 0.01);
```

```
RANDOM gamma_site ~ NORMAL(0, VAR = sigma_site) SUBJECT = siteid;
```

```
mu1 = p1 + beta0 + beta1*stratan + beta2*Base + beta3*age + beta4*sexn + beta5*addpwr +
Gamma_site;
```

```
mu2 = p1 - p2 + beta0 + beta1*stratan + beta2*Base + beta3*age + beta4*sexn + beta5*addpwr +
Gamma_site;
```

```
MODEL aval ~ MVN(mu, sigma);
```

```
BEGINNODATA;
```

```
Hyperopes 2wk = p1 + beta0 + beta1 + 0.5*beta4;
Myopes 2wk = p1 + beta0 + 0.5*beta4;
Hyperopes_3Day = p1 - p2 + beta0 + beta1 + 0.5*beta4;
Myopes_3Day = p1 - p2 + beta0 + 0.5*beta4;
```

```
ENDNODATA;
```

```
RUN;
```

Where,

CR-6400, Statistical Analysis Plan Version 1.0

Ads = Analysis dataset for CLUE Vision Scores  
 Stratan=numerical representation of strata, where Hyperopes=1 and Myopes=0  
 Base= Baseline CLUE Vision Score  
 Age= Age of subject at time of consent  
 Sexn=numerical representation of sex, where Female=1 and Male=0;  
 Addpwr=Add power of subject at baseline  
 Siteid=Site Identifier

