#### **CLUE Vision**

CLUE vision scores will be analyzed using a multivariate Bayesian normal random effects model. The model will include baseline clue score, age, add power, gender and strata (Hyperopes and Myopes) as fixed effects. Site will be included as a random effect. An unstructured (UN) covariance structure will be used to model the residual errors from measurements within the same subject across timepoints. Heterogeneous residuals covariance structures (R-side) across strata will be considered when appropriate.

The Model:

Let  $y_{ijk} = (y_{1ijk}, y_{2ijk})^T$  denote the CLUE vision scores for the  $K^{th}$  subject at the  $J^{th}$  site, in  $i^{th}$  stratum (Hyperope or Myope) at the 3-Day and 2-Week Follow-up evaluations. The likelihood for  $y_{ijk}$  is constructed as follows:

$$y_{ijk} \sim N(\mu_{ijk}, \Sigma)$$

$\mu_{ijk} = (\mu_{1ijk}, \mu_{2ijk})^T$  and  $\Sigma$  is a 2X2 variance-covariance matrix. Here,

$$\begin{aligned}\mu_{1ijk} &= \pi_1 + \mu_0 + \beta_1 Baseline_k + \beta_2 age_k + \beta_3 stratum_k + \beta_4 Gender_k + \beta_5 ADD_k + \gamma_j \\ \mu_{2ijk} &= \pi_2 + \mu_0 + \beta_1 Baseline_k + \beta_2 age_k + \beta_3 stratum_k + \beta_4 Gender_k + \beta_5 ADD_k + \gamma_j\end{aligned}$$

In this model  $\pi_1, \pi_2$ , represent the effect of time point with the constraint  $\pi_1 + \pi_2 = 0$ . In this model, we define  $stratum_k = 0$  for the Myope Strata and  $stratum_k = 1$  for the Hyperope Strata. So  $\beta_3$  stands for the difference between the Hyperope and Myope Strata with respect to CLUE vision; A positive  $\beta_3$  indicates the Hyperopes performed better than the Myopes.

We assume random site effects are independent and identically distributed (i.i.d) as  $\gamma_j \sim N(0, \sigma_{site}^2)$  for site for  $j=1, 2, 3, 4, 5, \dots, 11$  (site) . For the  $\beta$  coefficients, independent non-informative

**CR-6400**, Statistical Analysis Plan Version 1.0

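### The SAP's CLUE code labels the first follow-up's mean as the 2-week result, so on the SAP's own visit order both CLUE co-primary tests would be read at 3 days

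*SAP*

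**What the plan says.** SAP 5.1 sets hypotheses 1 and 2 at about 2 weeks of wear, with thresholds of 40 (myopes) and 32 (hyperopes). The decision rules in SAP 11.1 require the lower limit of the 95% credible interval for each stratum mean to exceed its threshold. The SAP introduction makes the SAP the final analysis guidance, overriding the protocol's statistical section.

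The CLUE program in SAP 14.2.1 contains:

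- the response vector: "ARRAY aval[2] FU1 FU2";
- a first mean, `mu1`, with time term `p1`, and a second mean whose line begins "mu2 = p1 - p2 + beta0 + beta1*stratan";
- the 2-week outputs: "Hyperopes 2wk = p1 + beta0 + beta1 + 0.5*beta4" and "Myopes 2wk = p1 + beta0 + 0.5*beta4";
- the 3-day hyperope output: "Hyperopes_3Day = p1 - p2 + beta0 + beta1 + 0.5*beta4", with a matching myope line.

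The variable list under the program defines the other inputs, for example "Base= Baseline CLUE Vision Score", but neither FU1 nor FU2, and it mentions no centring.

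On visit order, SAP 11.1 defines the two-element response vector "at the 3-Day and 2-Week Follow-up evaluations". The schedule in SAP 14.1 heads the day-3 visit "Visit 2 Treatment 1 Follow-up 1 Optimization" and gives the name Follow-up 2 to Visit 3.

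**The concern.** The quantities labelled as 2-week means appear to be built from the first response, and everything else in the SAP suggests that the first response is the 3-day score. If so, a program run as printed answers a different question from the one in the hypotheses, and nothing in the output would show it.

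The visits are not interchangeable. In protocol 7.2 the Visit 2 CLUE questionnaire is step 2.4 and the decision whether to modify the lenses is step 2.9. A 3-day score can therefore describe lenses that are then replaced, whereas the design rationale (protocol 4.2) is about 2 weeks in the final optimized pair. Two of the seven co-primary hypotheses are affected, and all seven must be met.

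**Working it through.** **1. Which response each output describes.** The model statement links the response array (FU1, FU2) to the mean array (`mu1`, `mu2`) element by element. With covariates at zero and sex at 0.5:

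| Output label | Time term | Same time term as |
|---|---|---|
| Hyperopes, 2 weeks | `p1` | `mu1`, so FU1 |
| Myopes, 2 weeks | `p1` | `mu1`, so FU1 |
| Hyperopes, 3 days | `p1 - p2` | `mu2`, so FU2 |
| Myopes, 3 days | `p1 - p2` | `mu2`, so FU2 |

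This follows from the code alone.

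**2. Which visit is FU1.** The schedule's Follow-up 1 and Follow-up 2 names and the vector order in SAP 11.1 both put 3 days first. SAP Table 3 also lists the visits in that order. Then `p2` = E[FU1] − E[FU2] = 3-day mean − 2-week mean, and each output labelled 2-week differs from the correct one by exactly `p2`.

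**3. Numerical check of the labels.** In 2,000 simulated trials (30 per stratum, least-squares fit of the printed mean structure, centred covariates) the true 2-week means were set at 47.71 (hyperopes) and 56.46 (myopes). With 3-day scores 5 points lower, the outputs labelled 2-week averaged 42.8 and 51.5, and those labelled 3-day averaged 47.7 and 56.4. With 3-day scores 10 points lower, the pairs were 37.7 and 46.5, and 47.7 and 56.5. Each label returned the other visit's mean.

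**4. The plan's power figure.** Inputs are the means and SDs in SAP Table 5 (47.71, SD 17.514; 56.46, SD 19.227), n = 30 per stratum, one-sided 0.025, df 29 and critical t 2.045. Noncentrality is λ = (mean − threshold)/(SD/√30).

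- Hyperopes: SE = 17.514/5.477 = 3.198; λ = 15.71/3.198 = 4.91; power 99.7%.
- Myopes: SE = 19.227/5.477 = 3.510; λ = 16.46/3.510 = 4.69; power 99.5%.

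Both agree with the 99% in SAP Table 8.

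**5. What the swap could do.** The documents give no 3-day CLUE mean, so the shifts below are assumptions. They also assume centred covariates and a one-sample t-test. For scale, SAP 4 equates 5 points with a 10% shift in the score distribution.

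*2-week means at planning values, 3-day scores lower:*

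| 3-day deficit | λ hyperopes | Pass | λ myopes | Pass | Both pass (product) |
|---|---|---|---|---|---|
| 0 | 4.91 | 99.7% | 4.69 | 99.5% | 99% |
| 5 | 3.35 | 90% | 3.26 | 88% | 79.5% |
| 10 | 1.79 | 41% | 1.84 | 43% | 17.5% |

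*2-week mean exactly at the threshold (nominal pass rate 2.5%), 3-day scores higher:*

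| 3-day excess | λ hyperopes | False pass | λ myopes | False pass |
|---|---|---|---|---|
| 5 | 1.56 | 33% | 1.42 | 28% |
| 10 | 3.13 | 86% | 2.85 | 79% |

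**6. A second gap in the same lines.** The fitted means contain baseline CLUE, age and ADD terms; the four outputs do not. Unless those covariates are centred, each output is a prediction at baseline CLUE 0, age 0 and ADD 0, which is neither visit's mean.

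**The case against.** The best defence is that FU1 is undefined, so the reversal is inferred. The output lines are the only ones in the program that name a visit, and they are consistent with FU1 being the 2-week score, with the primary visit as reference and the other as a difference. The code is also no transcription of SAP 11.1: its time effects are parameterised differently and its coefficients numbered differently, so the vector order need not carry over. That makes the conclusion conditional. But the labels are the very thing in dispute, and nothing else in the documents puts 2 weeks first. Even if the dataset did, the SAP would need to say so, because a programmer following its visit names would get the wrong answer.

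Other points have force. The hypothesis text is right and the defect is confined to the appendix code. The illustrative shifts have no source in the documents. If 3-day scores are lower because they precede optimization, the swap produces false failures rather than false passes; the false-pass table applies only in the other direction. The joint rates assume independent strata.

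Finally, `p2` is common to both strata. If the strata changed differently, say hyperopes by 10 points and myopes by 0, equal-weight least squares would give a common change of 5, and correctly labelled 2-week outputs would still be off by 2.5 points per stratum. That comes from a separate matter: the timepoint-by-strata interaction in protocol 14.5 is absent from the SAP model and code. It does not rescue the labels.

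**Conclusion.** The concern holds. It is certain that the outputs labelled 2-week carry FU1's time term and those labelled 3-day carry FU2's. Given FU1 = 3-day and FU2 = 2-week, the order used everywhere else in the SAP, both CLUE co-primary tests run as printed would be decided on the 3-day time term, against SAP 5.1.

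Under the SAP's own model of a common change over time, the error is exactly the 3-day minus 2-week difference in mean CLUE. Its size and direction cannot be obtained from the documents: a difference near zero is harmless, and one of 5 to 10 points could turn either test in either direction. The pass rates rest on assumed shifts, centred covariates, the planning values and a one-sample t-test. Since the code may determine which visit decides two co-primary tests, it should be corrected before it is run.

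**What to change.** In SAP 14.2.1:

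1. Define FU1 as the 3-day and FU2 as the 2-week CLUE vision score in the variable list.
2. Give both 2-week outputs the time term `p1 - p2` and both 3-day outputs the time term `p1`. Alternatively, code the time effect with the sum-to-zero constraint already written in SAP 11.1 and build each output from its own visit's term.
3. Centre baseline CLUE, age and ADD, or add their terms to the outputs at the sample means, so that the outputs are adjusted visit means. Exchanging the time terms alone does not achieve this.

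The cost is one definition line, four output lines and a centring step. Data collection, visits and sample size do not change, and the stated power does not depend on this code.

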### Visual Performance

```

PROC MCMC DATA =ads vp NTHREADS=12 SEED=20180906 NBI=80000 NMC=150000
THIN=30 DIAG=ALL OUTPOST=simout DIC PLOTS(SMOOTH FRINGE)=ALL
MCHISTORY=BRIEF PROPCOV=QUANEW STATS=ALL STATS(ALPHA = (0.05)
PERCENTAGE=(2.5 50 97.5)) plots(smooth)=ALL MONITOR=(parms_ mu_D mu_I
mu_N);

PARMS beta0 0 beta1 0 beta2 0 beta3 0 beta4 0 beta5 0 beta6 0;
```

```

PARMS s2 1;
```

```

PARMS s2g_site s2g_site1;
```

```

PRIOR beta: ~ NORMAL(0, var = 1000);
PRIOR s2 ~ IGAMMA(.001, s =.001);
PRIOR s2g_site s2g_subj~ IGAMMA(.001, s =.001);
```

```

RANDOM Gamma site ~ NORMAL(0, VAR = s2g_site) SUBJECT=SITEID;
RANDOM Gamma_subj ~ NORMAL(0, VAR = s2g_subj) SUBJECT=USBJID;
```

```

mu = beta0 + beta1*dist_yn + beta2*inter_yn + beta3*age + beta4*sexn + beta5*stratan +
beta6*addpwr + Gamma_subj + Gamma_site;
```

```

MODEL AVAL ~ NORMAL (mu, VAR = s2);
```

```

BEGINNODATA;
  mu_D = beta0 + beta1 + 0.5*beta4 + 0.5*beta5;
  mu_I = beta0 + beta2 + 0.5*beta4 + 0.5*beta5;
  mu_N = beta0 + 0.5*beta4 + 0.5*beta5;
ENDNODATA;
```

```

RUN;
  
```

Where,

ads vp = Analysis dataset for Binocular HLHC Visual Performance  
 dist\_yn= numerical representation of position, where distance=1 and Intermediate and Near=0  
 inter\_yn= numerical representation of position, where Intermediate=1 and Distance and Near=0  
 Stratan=numerical representation of strata, where Hyperopes=1 and Myopes=0

CR-6400, Statistical Analysis Plan Version 1.0

Age= Age of subject at time of consent

Sexn=numerical representation of sex, where Female=1 and Male=0;

Addpwr=Add power of subject at baseline

Siteid=Site Identifier

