3.2. Inclusion Criteria

Potential subjects must satisfy all of the following criteria to be enrolled in the study:

Inclusion Criteria after Screening:

1. The subject must read, understand, and sign the STATEMENT OF INFORMED CONSENT and receive a fully executed copy of the form.
2. The subject must appear able and willing to adhere to the instructions set forth in this clinical protocol.
3. The subject must be at least 40 years of age and not greater than 70 years of age at the time of consent.
4. Subjects must own a wearable pair of spectacles if required for their distance vision.
5. The subject must be an adapted soft contact lens wearer in both eyes (i.e. wears lenses a minimum of 2 days per week for at least 6 hours per wear day, for 1 month of more duration).
6. The subject must either already be wearing a presbyopic contact lens correction (e.g., reading spectacles over contact lenses, multifocal or monovision contact lenses, etc.) or if not respond positively to at least one symptom on the “Presbyopic Symptoms Questionnaire” (Appendix E).

Inclusion Criteria after Baseline:

7. The subject's distance spherical equivalent refraction (vertex corrected if ≥ -4.25 D) must be in the range of -1.25 D to -5.75 D or +0.75 D to +3.25 D in each eye.
8. The subject's refractive cylinder must be ≤ 0.75 D in each eye.
9. The subject's ADD power must be in the range of +0.75 D to +2.50 D.
10. The subject must have distance best corrected visual acuity of 20/20⁻³ or better in each eye.

Clinical Study Protocol

Johnson & Johnson Vision Care, Inc.

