### CLUE Overall Quality of Vision

Overall comfort scores will be assessed using the Contact Lens User Experience (CLUE™) questionnaire after approximately 2 weeks of lens wear. CLUE is a validated patient-reported outcomes questionnaire to assess patient-experience attributes of soft, disposable contact lenses (comfort, vision, handling, and packaging) in a contact-lens wearing population in the US, ages 18-65. Derived CLUE™ scores using Item Response Theory (IRT) follow a normal distribution with a population average score of 60 (SD 20), where higher scores indicate a more favorable/positive response with a range of 0-120. A 5-point increase in an average CLUE™ score translates into 10% shift in the distribution of scores for population of soft contact lens wearers.

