## 7. DEFINITIONS AND DERIVED VARIABLES

### 7.1. Age

Age will be calculated using the Date of Birth (DOB) and the date of the consenting the subject and presented as age at last birthday as an integer.

Age = Integer part of [(Date of Baseline visit – Date of Birth) / 365.25]

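### The SAP code tests five of the seven co-primary means at age 0 and ADD 0 (and, for CLUE, baseline score 0), not at the population mean in the hypotheses

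*SAP*

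**What the plan says.** Hypotheses 1 to 5 (SAP 5.1) concern mean CLUE vision in myopes and in hyperopes, and mean binocular logMAR at distance, intermediate and near. SAP 11.1 decides each one from a 95% credible bound on that mean. SAP section 1 makes the SAP the final guidance, ahead of the protocol's statistical section.

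The code is in SAP 14.2.1.

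- **VA.** The linear predictor contains `beta3*age` and ends with "beta6*addpwr + Gamma_subj + Gamma_site". The monitored distance mean is "mu_D = beta0 + beta1 + 0.5*beta4 + 0.5*beta5". The intermediate and near means have the same form, with no age or ADD term.
- **CLUE.** The predictor is "mu1 = p1 + beta0 + beta1*stratan + beta2*Base + beta3*age + beta4*sexn + beta5*addpwr" plus the site effect. The monitored myope mean is "Myopes 2wk = p1 + beta0 + 0.5*beta4", and the hyperope mean adds only `beta1`. Baseline score, age and ADD are all absent.

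The variable lists define these covariates plainly, for example "Base= Baseline CLUE Vision Score". SAP 7.1 derives age in years, "presented as age at last birthday as an integer". No passage mentions centring or a reference value.

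The eligible population is aged 40 to 70, and the subject's "ADD power must be in the range of +0.75 D to +2.50 D" (Protocol 3.2). CLUE scores run from 0 to 120 and "follow a normal distribution with a population average score of 60 (SD 20").

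**The concern.** Leaving a term out of the monitored quantity sets that covariate to zero. Age 0 and ADD 0 cannot occur in this trial. Baseline CLUE 0 is the bottom of the scale, 3 SD below its stated average: (60 − 0)/20 = 3. The code does set sex to 0.5, and stratum to 0.5 for VA, which suggests that a population average was intended and the continuous covariates were overlooked.

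Three things follow:

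1. The tested value is shifted from the true mean by slope × covariate mean.
2. Its interval widens, because it is an extrapolation far outside the data.
3. For CLUE, the N(0, 1000) priors pull the poorly identified intercept towards 0.

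Depending on slopes nobody knows in advance, a lens that meets its targets may usually fail, or a lens at a VA limit may pass. All seven co-primary tests must succeed, so the trial's conclusion depends on these lines.

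**Working it through.** **1. Stated power, reproduced.** Inputs: means and SDs from SAP Table 5, SD 0.11 for every VA position, n = 60 for VA and 30 per stratum for CLUE. Power = Φ(|mean − threshold|/(SD/√n) − 1.96).

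- Near VA: SE = 0.11/√60 = 0.0142; 0.093/0.0142 = 6.5; power about 100%. Distance and intermediate lie further from their limits.
- Hyperopes: 15.71/(17.514/√30) = 15.71/3.20 = 4.91; power 99.8%.
- Myopes: 16.46/(19.227/√30) = 16.46/3.51 = 4.69; power 99.7%.

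These agree with SAP Table 8. That power belongs to the mean at the sample's own covariate values.

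**2. What the code tests.**

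- VA: coded value = mean − b_age × mean(age) − b_ADD × mean(ADD).
- CLUE: the same, less b_base × mean(Base).

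**3. Loss of precision, from the age range alone.** In a one-outcome regression with flat priors, SE at age 0 ÷ SE at mean age = √(1 + (mean/SD)²). For ages within 40–70 the largest SD at mean m is √((m − 40)(70 − m)). The ratio mean/SD is smallest at m = 50.9, where SD = 14.4 and mean/SD = 3.53. The SE therefore grows at least √(1 + 3.53²) = 3.67-fold. For near VA with no age slope, SE is at least 0.0142 × 3.67 = 0.052, and power is at most Φ(0.093/0.052 − 1.96), about 43%. Fitting the three positions jointly with a common age slope gives about 58% at between-position correlation 0.5 and 82% at 0. This uses the most favourable age mix possible (about 64% aged 40 and 36% aged 70) and ignores ADD.

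**4. A plausible age mix.** Assume mean age 53.9, SD 5.4, between-position correlation 0.5, and leave ADD out.

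- Variance of the age slope = 0.11² × (1 + 2 × 0.5)/3 ÷ (60 × 5.4²) = 4.61 × 10⁻⁶, so its SD is 0.00215.
- SD of the coded mean = √((53.9 × 0.00215)² + 0.0142²) = 0.117.
- Pass rates with no slope: distance Φ(0.177/0.117 − 1.96) = 33%; intermediate Φ(0.224/0.117 − 1.96) = 48%; near Φ(0.093/0.117 − 1.96) = 12%.
- A slope of 0.003 logMAR per year shifts the coded mean by −0.003 × 53.9 = −0.16.

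**5. Simulation with the SAP priors** (300 trials per scenario, Monte Carlo error up to 3 points). Assumptions not in the documents: age as in step 4; ADD mean 1.68, SD 0.41, correlation 0.50 with age; baseline CLUE 55 (SD 20), correlated 0 or 0.5 with follow-up; 60% women, no sex effect; 11 sites with SD 3 CLUE points or 0.015 logMAR; correlation 0.6 between CLUE visits. The VA code gives `s2g_site1` no prior and never declares `s2g_subj`; they were read as one parameter.

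| Age slope per year (VA; CLUE) | VA pass at Table 5 means (distance/intermediate/near) | VA pass with true mean at the threshold | CLUE pass |
|---|---|---|---|
| 0; 0 | 34/45/14% | 2–3% | 0–3% |
| 0.003; −0.5 | 76/84/52% | 32–33% | 7–24% |
| 0.006; −1 | 99/100/93% | 76–77% | 42–70% |
| Evaluated at covariate means | 100% | at most 1% | 99–100% |

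Posterior SD as coded against corrected: VA 0.126 against 0.019; CLUE 17–21 against 2.7–3.3 points. With variances treated as known, VA gives 0.122 against 0.014.

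**6. Bias in CLUE (hyperopes, true mean 47.7, no age slope).** At baseline correlation 0.5 the slope is 0.5 × 18.4/20 = 0.46, where 18.4 is the average of the two stratum SDs. The shift is 0.46 × 55 = 25.3 points. The coded mean is 17.8, so about 4.5 further points come from the priors. At correlation 0 it is 34.8, but 46.1 with near-flat priors, so most of that gap is shrinkage.

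**7. Other slopes.** A simpler simulation (4,000 trials per scenario; age 55, SD 7; ADD 1.75, SD 0.5; no site effect) gave these results:

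- VA age slope −0.002: pass rates of 8% (distance) and 1% (near).
- True near mean 0.20, which fails the 0.17 limit, with slope 0.005: passes in 51% of trials, and in 78% with an added ADD slope of 0.04 per dioptre. At the sample means it passes in about 0%.

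**8. All five efficacy tests together** (VA and CLUE taken as independent). For a lens at the Table 5 values, all five pass in about 0.3%, 1–11% and 39–61% of trials for the three slope rows, against about 98% or more corrected. If only near VA is truly at 0.17, all five pass in about 1–6% (second row) or 32–50% (third row).

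**The case against.** The analysis datasets may hold centred covariates, in which case dropping the continuous terms would be right. Averaging the binary covariates while omitting the continuous ones is what such code would look like, and SAP 7.1 governs how age is presented rather than how it is scaled in the model. This cannot be excluded. But no passage says it, the variable lists name the plain variables, and a programmer following the SAP would use them. If centring was intended, it still has to be written down.

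The appendix also departs from SAP 11.1 elsewhere. For VA, a subject random effect replaces the unstructured covariance. For CLUE, the time parameters differ. One could therefore argue that the correctly worded means in 11.1 should prevail. Nothing ranks the two, and 11.1 does not say at which covariate values its means are taken.

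The objections to the magnitude stand in part. The pass rates rest on assumed covariates and slopes. High false-pass rates need acuity to worsen with age; with no slope the VA false-pass rate is 2–3%, about nominal, and the 32–77% figures are per test. No CLUE false-pass rate was computed. The corrected VA SD differs between the two calculations, so the widening is 0.126/0.019 = 6.6-fold or 0.122/0.014 = 8.7-fold. The descriptive means required by SAP 8.2 would probably expose a wildly displaced CLUE estimate, but only after the data are in hand.

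**Conclusion.** The concern holds. On the printed code, five of seven co-primary tests (three VA, two CLUE) evaluate an extrapolation outside the eligible population instead of the mean in the hypothesis. That is algebra and needs no assumption beyond covariates entered as the SAP defines them. A large loss of precision follows from the 40–70 age range alone: at least 3.67-fold in a one-outcome regression with flat priors. The stated power of 99% or more does not apply to the coded tests.

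The simulated pass rates are illustrations, not the trial's operating characteristics. The direction of the error depends on unknown slopes: a lens that meets its targets can fail, and where VA worsens with age or ADD, a lens at or beyond a VA limit can pass. This must be settled before database lock, because a correction made after seeing results would be a post hoc change to primary tests.

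**What to change.** State the covariate reference values in SAP 11.1 and code them in 14.2.1.

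- **VA:** add `beta3*mean(age) + beta6*mean(addpwr)` to `mu_D`, `mu_I` and `mu_N`.
- **CLUE:** add `beta2*mean(Base) + beta3*mean(age) + beta5*mean(addpwr)` to each stratum mean, using that stratum's own covariate means. Pooled means would give an adjusted stratum mean, which is a different quantity from the one in hypotheses 1 and 2.
- Equivalently, centre these covariates before PROC MCMC (within stratum for CLUE) and say so.
- State whether sex is deliberately fixed at 0.5 or set to the observed share.

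While editing the CLUE lines, resolve a separate point. The 2-week quantities use the predictor for the first element of the outcome vector (FU1), whereas SAP 11.1 lists the 3-day visit first. If FU1 is the 3-day visit, a corrected contrast would still test the wrong visit.

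The cost is a few lines of SAP text and code, with no change to visits, data collection or sample size. In the checks above, the corrected contrasts return pass rates of 99–100% at the Table 5 means, in line with the stated power.
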